4.2 Therapy Delivery Map – CDX-011

Page 1 of 2

4.2.1 Therapy Delivery Map – All Cycles of CDX-011	Each cycle lasts 3 weeks (21 days). Treatment may continue for up to 14 months or 18 cycles, whichever occurs first. One cycle of treatment is described in this TDM. This TDM is on 2 pages. Use a copy of this page once for each cycle (please note cycle number below).	Patient COG ID number _____ DOB _____
---	---	--

Begin CDX-011 therapy only when ANC \geq 1000/ μ L; Platelets \geq 75,000/ μ L (transfusion independent); Hemoglobin \geq 8.0 g/dL (RBC transfusions allowed); Cr clearance or radioisotope GFR \geq 70 mL/min/1.73 m² or a serum creatinine based on age/gender as per [Section 4.2.3](#); Total bilirubin \leq 1.5 x ULN for age; SGOT (AST) or SGPT (ALT) \leq 110 U/L, and Serum albumin $>$ 2 g/dL.

DRUG	ROUTE	DOSAGE	DAY	IMPORTANT NOTES
CDX-011 (glembatumumab vedotin) IND# 128248	IV over 90 minutes	1.9 mg/kg/dose	Day 1	Recalculate the dose prior to each infusion. Round dose to the nearest 1 mg. See Section 4.2.3 for complete details.

Enter Cycle #: _____

Ht _____ cm

Wt _____ kg

BSA _____ m²

Date Due	Date Given	Day	CDX-011 ____ mg	Studies
			Enter calculated dose above and actual dose administered below	
		1	mg	a-l
		8*		(a-f)*
		21		g, h, i

Start the next cycle on Day 22 or as soon as starting criteria are met, whichever occurs later. Treatment should continue up to 14 months (or 18 cycles, whichever occurs first) in the absence of disease progression or unacceptable toxicity. If disease progression or unacceptable toxicity occurs, the patient will be taken off protocol therapy.

Note: Patients who receive surgery or radiation on any site of measurable disease prior to completion of the 6th cycle of therapy will be taken off protocol therapy.

* Cycle 1 only

See Section 5.0 for Dose Modifications for Toxicities and the COG Member website for Supportive Care Guidelines.

All Cycles

Page 2 of 2

4.2.2 Required Observations Prior to Cycle 1 and During All Cycles

All baseline studies must be performed prior to starting protocol therapy unless otherwise indicated below. For Cycle 1 only, observations a-f can be performed up to 7 days before the start of therapy and imaging studies may be obtained within 2 weeks prior to the start of therapy.

- a. Hx/PE/Wt /Ht. Prior to each cycle and on Day 8 of Cycle 1.
- b. CBC/diff/platelets. Prior to each cycle and on Day 8 of Cycle 1.
- c. Bilirubin & Creatinine. Prior to each cycle and on Day 8 of Cycle 1.
- d. Electrolytes, BUN, Ca⁺⁺, PO₄, Mg⁺⁺. Prior to each cycle and on Day 8 of Cycle 1.
- e. AST, ALT, albumin. Prior to each cycle and on Day 8 of Cycle 1.
- f. Neurologic evaluation. Prior to each cycle and on Day 8 of Cycle 1. Assess for NCI CTCAE > Grade 2 neuropathy.
- g. CT chest. Prior to Cycle 1 and following Cycles 2, 4, 6 and every 3rd cycle thereafter.
- h. Tumor disease evaluation. Prior to Cycle 1 and following Cycles 2, 4, 6, and every 3rd cycle thereafter. Evaluations should include CT or MRI of all lesions meeting eligibility criteria. Use the same imaging modality for all disease evaluations. Patients who had a RECIST response (CR or PR) at Cycle 6 imaging evaluation are required to have a confirmatory scan following Cycle 8. For patients who undergo a surgical resection following Cycle 6, either a CT scan or MRI post-surgery to establish a new baseline is strongly recommended prior to re-initiating CDX-011 therapy. See [Section 16.0](#) for details.
- i. ¹⁸FDG PET or Bone Scan. Prior to Cycle 1 and following Cycles 2, 4, 6, and every 3rd cycle thereafter. ¹⁸FDG PET or bone scan is required at baseline. ¹⁸FDG PET scan is an optional study, but if completed then a bone scan is not necessary. It is recommended to obtain MRI or CT scan of any lesion positive on bone or ¹⁸FDG PET scan. Bone or ¹⁸FDG PET scan is required to assess for new disease after Cycles 2, 4 and 6. Further bone scan or ¹⁸FDG PET should be completed as clinically indicated at investigator discretion. For consistency, investigators are encouraged to utilize the same modality used at baseline to follow positive lesions that are identified with ¹⁸FDG PET or bone scan. See [Section 16.0](#) for details.
- j. Pharmacokinetics. Cycle 1 only, Day 1 pre-dose, end of infusion, 1, 2, 4, 8 and 24 (+/- 4 hours) hours post infusion, 4 days (+/- 1 day) post infusion, 7 and 21 days post infusion. Required for the first 6 evaluable patients \leq 14 years of age enrolled at COG sites. Optional for patients $>$ 14 years of age and \leq 21 years of age enrolled at COG sites. See [Section 15.2](#) for details.
- k. Tumor GPNMB expression (required). Submission of a formalin-fixed, paraffin-embedded (FFPE) sample of tumor tissue (block or 10 slides) from the most recent surgery (preferred) or from any previous biopsy or resection is mandatory within 4 weeks of enrollment. See [Section 15.1](#) for details.
- l. Pregnancy test. Prior to Cycle 1. Female patients of childbearing potential require a negative pregnancy test prior to starting treatment; sexually active patients must use an acceptable method of birth control.

This listing only includes evaluations necessary to answer the primary and secondary aims. OBTAIN OTHER STUDIES AS REQUIRED FOR GOOD CLINICAL CARE.

Comments (Include any held doses, or dose modifications)

All Cycles

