1.2 Secondary Aims

1.2.1 To assess the feasibility and toxicity profile of CDX-011 in patients with recurrent osteosarcoma.

1.2.2 To describe the pharmacokinetics of CDX-011 in adolescents and young adults with recurrent osteosarcoma enrolled at COG sites and COG Phase 1 Consortium sites only.

1.2.3 To determine if there is a relationship between tumor GPNMB expression by IHC and response to CDX-011 therapy.

1.2.4 To estimate, in the cohort of patients previously treated with eribulin, the proportion who will experience disease progression during the first 4 months of CDX-011 therapy and the proportion of patients who experience a RECIST-defined complete or partial response.

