10.0 EVALUATION CRITERIA

10.1 Common Terminology Criteria for Adverse Events (CTCAE)

This study will utilize version 4.0 of the CTCAE of the National Cancer Institute (NCI) for toxicity and performance reporting. A copy of the CTCAE version 4.0 can be downloaded from the CTEP website

(http://ctep.cancer.gov/protocolDevelopment/electronic_applications/ctc.htm).

Additionally, toxicities are to be reported on the appropriate case report forms.

Please note: 'CTCAE v4.0' is understood to represent the most current version of CTCAE v4.0 as referenced on the CTEP website (ie, v4.02 and all subsequent iterations prior to version 5.0).

10.2

Response Criteria for Patients with Solid Tumors

For the purposes of this study, patients should be evaluated for response following Cycles 2, 4 and 6 and following every 3rd cycle thereafter. Patients who have a RECIST response (CR or PR) at Cycle 6 will have confirmatory imaging after Cycle 8.

Response and progression will be evaluated in this study using the new international criteria proposed by the revised Response Evaluation Criteria in Solid Tumors (RECIST) guideline (version 1.1).⁵¹ Changes in the largest diameter (unidimensional measurement) of the tumor lesions and the shortest diameter in the case of malignant lymph nodes are used in the RECIST criteria.

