11.5.2 Special Situations as Exceptions to Expedited Reporting

An expedited report may not be required for a specific protocol where an AE is listed as expected. The exception or acceptable reporting procedures will be specified in the protocol. The protocol specific guidelines supersede the NCI Adverse Event Reporting Guidelines. These special situations are listed under the CTEP-AERS reporting table for this protocol.

11.6 **Reporting Requirements - Investigator Responsibility**

Clinical investigators in the treating institutions and ultimately the Study Chair have the primary responsibility for AE identification, documentation, grading, and assignment of attribution to the investigational agent/intervention. It is the responsibility of the treating physician to supply the medical documentation needed to support the expedited AE reports in a timely manner.

Note: All expedited AEs (reported via CTEP-AERS) must also be reported via routine reporting. Routine reporting is accomplished via the Adverse Event (AE) Case Report Form (CRF) within the study database.

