11.9 Protocol Specific Additional Instructions and Reporting Exceptions

- **Grades 1- 4 myelosuppression (anemia, neutropenia, thrombocytopenia) do not require expedited reporting.**
- **Grades 1-2 peripheral neuropathy do not require expedited reporting.**

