11.10 Routine Reporting of Adverse Events

Note: The guidelines below are for routine reporting of study specific adverse events on the COG case report forms and do not affect the requirements for CTEP-AERS reporting.

Routine reporting is accomplished via the Adverse Event (AE) Case Report Form (CRF) within the study database. For this study, routine reporting will include all CTEP-AERS reportable events and Grade 3 and higher non-hematologic and Grade 4 and higher hematologic Adverse Events

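### Sections 11.9 and 11.10 require no adverse-event form entry for new Grade 2 peripheral neuropathy, so the required data for Aim 1.2.1 need not show how often it occurs

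*Combined protocol and SAP*

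**What the plan says.** Aim 1.2.1 (Section 1.2) is "To assess the feasibility and toxicity profile of CDX-011 in patients with recurrent osteosarcoma". Section 4.2.2 lists the required observations and describes its own scope: "This listing only includes evaluations necessary to answer the primary and secondary aims". Item f on that list is a neurologic evaluation before each cycle and on Day 8 of Cycle 1, with the instruction "Assess for NCI CTCAE > Grade 2 neuropathy".

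Three reporting provisions then apply:

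- Section 11.9, on expedited reports: "Grades 1-2 peripheral neuropathy do not require expedited reporting".
- Section 11.10, on the routine adverse-event form: "routine reporting will include all CTEP-AERS reportable events and Grade 3 and higher non-hematologic and Grade 4 and higher hematologic Adverse Events".
- Section 10.1, in general terms and with no grade: "toxicities are to be reported on the appropriate case report forms".

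Grade 2 matters elsewhere in the plan. Section 3.2.7.1 admits patients with neuropathy up to Grade 2 on the Modified Balis scale. Section 5.1.1.2 makes a Grade 2 non-hematologic toxicity dose-limiting if it lasts at least 7 days and requires treatment interruption. Section 5.1 sends any suspected or confirmed dose-limiting toxicity to the Study Chair within 24 hours.

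**The concern.** The protocol singles out neuropathy: it sets an entry limit, prints a grading scale in 5.2 and schedules an examination every cycle. The drug carries a microtubule inhibitor, 2.4 says there are no data in children, and treatment may run to about 18 cycles (4.1). On the printed Balis scale, Grade 2 includes altered gait or fine motor skills, which patients notice.

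Yet the reporting floor sits one grade higher. If sites follow the visible rules exactly, the repeated examination need not yield a reported Grade 2 rate, or a count of patients who moved from Grade 0-1 to Grade 2 on drug. A Grade 2 finding at entry may be on file, because 11.4.1 asks for baseline findings by CTCAE grade when possible, while the same grade arising on treatment need not be. What is at stake is how complete the toxicity description under Aim 1.2.1 will be.

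**Working it through.** The plan gives no figure on this point to reproduce. The check traces a new Grade 2 peripheral neuropathy through each visible rule that could require a record.

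| Rule | What it requires for new Grade 2 neuropathy |
|---|---|
| 4.2.2 item f | An examination; the only grade named is above 2, and no grade field is requested |
| 11.9 | No expedited report; the wording makes no exception for hospitalization |
| 11.10 | No routine entry: it is below Grade 3 and, given 11.9, not a CTEP-AERS event |
| 10.1 | Toxicities go on case report forms, but no grade is set; 11.10 is the visible text that sets it |
| 11.4.1 | Covers findings present at baseline; later reporting is tied to the expedited criteria |
| 11.4.2 | Says when to re-report a persistent event that worsens; it does not lower the floor in 11.10 |
| 5.1 with 5.1.1.2 | Notice to the Study Chair, only if the event lasts at least 7 days and requires interruption |

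The last row is the one route that clearly captures some Grade 2 events. A held dose can also be noted on the delivery map, which has a field headed "Comments (Include any held doses, or dose modifications". Neither is the adverse-event form, and 11.6 says "Routine reporting is accomplished via the Adverse Event (AE) Case Report Form (CRF) within the study database". Section 11.10 has no clause for dose-limiting toxicity, so a Grade 2 event does not enter that form merely by being dose-limiting. A Grade 2 event other than neuropathy could still enter by another route, for example if it led to hospitalization and so became CTEP-AERS reportable under 11.8.

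**Size.** The Grade 2 rate q is an assumption, taken from 0.05 to 0.30. The number of patients n is at most 38 (9.1).

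- Expected patients affected = n × q: 38 × 0.05 = 1.9; 38 × 0.30 = 11.4.
- Chance of at least one = 1 − (1 − q)^n: 1 − 0.95^38 = 0.86; 1 − 0.70^38 is above 0.99.

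The 38 allows for ineligible and inevaluable patients. With 29, the maximum of outcome-evaluable patients without prior eribulin, the expected number is 29 × 0.05 = 1.45 to 29 × 0.30 = 8.7, and the chance of at least one is 1 − 0.95^29 = 0.77 or more.

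**Recording load of the fix.** Scheduled evaluations = one per cycle + Day 8 of Cycle 1 + End of Therapy, with two grade fields each.

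- Leaves after Cycle 2: 2 × (2 + 1 + 1) = 8 entries.
- Leaves after six cycles: 2 × (6 + 1 + 1) = 16 entries.

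The End of Therapy visit matters. For a patient who leaves after Cycle 2, the item f evaluations fall before Cycle 1, on Day 8 of Cycle 1 and before Cycle 2. None follows the second dose.

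**The case against.** A Grade 3 floor for non-hematologic events is a legitimate choice, and 11.10 applies it to all of them alike. Aim 1.2.1 does not promise Grade 2 rates. The toxicity analysis in 9.5 is built on dose-limiting toxicities and treatment-related deaths, and no analysis in the documents needs a count of other Grade 2 events. The Grade 2 cases that interrupt treatment are already notified. All of this stands, and it makes the point an improvement rather than the correction of an error.

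The forms themselves are not shown, nor are most of 5.2 and the cycle-start criteria, and 10.1 leaves room for forms that collect more than 11.10 asks. That stands too: the conclusion is about what the visible rules require, not about what the database will hold.

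Two stronger readings are tempting, and the documents do not support either.

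- A reader might infer that item f tells sites to disregard Grade 2. It does not. Deciding whether a patient exceeds Grade 2 means grading the patient, and the cut resembles the entry limit in 3.2.7.1 (on a different scale), so it reads naturally as a safety check. History and physical examination are also due each cycle. The gap comes from 11.9 and 11.10; item f only fails to close it.
- A reader might infer that Grade 2 dose-limiting events escape the six-patient rule in 9.2 or the Bayesian monitor in 9.5. They need not, because the notices to the Study Chair can be counted.

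**Conclusion.** The point holds in a limited form. Under the visible text of 11.9 and 11.10, neither a new Grade 2 peripheral neuropathy nor a Grade 2 event that is merely dose-limiting requires an adverse-event form entry, and item f does not ask for the grade. The required adverse-event data for Aim 1.2.1 therefore need not show a Grade 2 neuropathy rate or a shift from baseline. Voluntary recording may fill part of this, but it could differ between sites.

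The size depends on a rate that the documents do not give. The 5% to 30% range is an illustration and carries no evidence about this drug. The primary endpoints, the 19+10 decision rule, the six-patient rule and the 9.5 monitor are unaffected. This is a cheap improvement to a secondary aim.

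**What to change.** - **Section 11.10:** add to routine reporting Grade 2 peripheral neuropathy and any Grade 2 event that meets the dose-limiting definition in 5.1.1.2. Keep the 11.9 exemption from expedited reporting.
- **Section 4.2.2 item f:** record the CTCAE v4.0 peripheral motor and peripheral sensory neuropathy grade, at all grades, at baseline and at each scheduled evaluation.
- **Section 7.1:** record the same two grades at the End of Therapy visit, which already has a history and physical examination.
- **Aim 1.2.1 analysis:** report the worst on-study grade against the baseline grade.

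The cost is two grade fields at examinations already planned (8 entries for a patient who leaves after Cycle 2, 16 after six cycles), a short addition to 11.10, and a few more adverse-event entries. No extra visit or test is needed. If the case report forms already collect these grades, only the wording of 11.10 and item f needs to change to match.

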4.2.3 Therapy During Cycle 1 and Subsequent Cycles

One cycle of CDX-011 treatment is described below. A cycle may be repeated every 21 days (3 weeks) if the patient has at least stable disease and has again met laboratory parameters as defined in the eligibility section, and detailed below.

CDX-011 (glembatumumab vedotin): Intravenously over 90 minutes

Day: 1

Dose: **1.9 mg/kg/dose.** Round doses to the nearest 1 mg.

[figure not shown]
Actual body weight will be recorded and used to calculate dose prior to each infusion. CDX-011 is to be diluted with D5W and administered using a 0.22 μ m low protein binding in-line filter. Patient should receive post-infusion flush with appropriate volume of D5W administered at the same rate as CDX-011 infusion.

Note: Premedication is not required, but may be used as clinically indicated.

Monitoring during CDX-011 infusion:

- Vital signs should be assessed every 15 minutes for the first hour of the infusion, followed by every 30 minute assessment for the remainder of the infusion and post-infusion flush. More frequent assessment may be required based on the patient's clinical condition.

Criteria to start each cycle

See Section 5.0 for Dose Modifications based on Toxicities.

All Cycles

5.0 DOSE MODIFICATIONS FOR TOXICITIES

5.1 Definition of Toxicities

NOTE: Any suspected or confirmed dose-limiting toxicity should be reported to the Study Chair within 24 hours of site knowledge of its occurrence.

5.1.1 Definition of Dose-Limiting Toxicity (DLT)

DLT will be defined as any of the following events that are possibly, probably or definitely attributable to protocol therapy.

Note: Dose limiting hematological and non-hematological toxicities are defined differently.

5.1.1.1 Hematological Dose Limiting Toxicity

[figure not shown]
- Grade 4 neutropenia for > 7 days
- Grade 4 febrile neutropenia
- Platelet count < 25,000/ μ L on 2 separate days, or requiring a platelet transfusion on 2 separate days, within a 7 day period
- Myelosuppression that causes a delay of > 14 days between treatment cycles.

5.1.1.2 Non-Hematological Dose-Limiting Toxicity

[figure not shown]
- Any Grade 3 or greater non-hematological toxicity, except for the following:
 - Grade 3 nausea and/or vomiting of < 3 days duration
 - Grade 3 or 4 fever < 5 days duration
 - Grade 3 infection < 5 days duration
 - Grade 3 rash < 5 days duration
 - Grade 3 pruritis < 5 days duration
 - Grade 3 fatigue < 5 days duration
 - Grade 3 non-hematologic laboratory abnormalities that resolve within 14 days to Grade 1, or to initial eligibility criteria, or to baseline (if the patient entered the study with existing toxicity). Note: for the purposes of this study the ULN for SGPT (ALT) is defined as 45 U/L.
 - Grade 3 infusion-related reactions < 24 hours duration (see [Section 5.2.3](#))
 - Grade 3 hypophosphatemia, hypokalemia, hypocalcemia, or hypomagnesemia responsive to oral supplementation.
- Any Grade 2 non-hematological toxicity that persists for \geq 7 days and is considered sufficiently medically significant or sufficiently intolerable by patients that it requires treatment interruption will also be considered a DLT.

[figure not shown]
5.2 Dose Modifications for Adverse Events

The Study Chair must be notified of any use of myeloid growth factor for hematologic toxicity and of any other dosage modification described below.

[figure not shown]
Modified (“Balis”) Pediatric Scale of Peripheral Neuropathies

[figure not shown]
Peripheral Motor Neuropathy:

- Grade 1: Subjective weakness, but no deficits detected on neurological exam, other than abnormal deep tendon reflexes.
- Grade 2: Weakness that alters fine motor skills (buttoning shirt, coloring, writing or drawing, using eating utensils) or gait without abrogating ability to perform these tasks.
- Grade 3: Unable to perform fine motor tasks (buttoning shirt, coloring, writing or drawing, using eating utensils) or unable to ambulate without assistance.
- Grade 4: Paralysis.

Peripheral Sensory Neuropathy:

- Grade 1: Paresthesias, pain, or numbness that do not require treatment or interfere with extremity function.
- Grade 2: Paresthesias, pain, or numbness that are controlled by non-narcotic medications (without causing loss of function), or alteration of fine motor skills (buttoning shirt, writing or drawing, using eating utensils) or gait, without abrogating ability to perform these tasks.
- Grade 3: Paresthesias or pain that are controlled by narcotics, or interfere with extremity function (gait, fine motor skills as outlined above), or quality of life (loss of sleep, ability to perform normal activities severely impaired).
- Grade 4: Complete loss of sensation, or pain that is not controlled by narcotics.

6.0 DRUG INFORMATION

6.1 CDX-011

(GLEMBATUMUMAB VEDOTIN, CR011-vcMMAE) NSC# 763737, IND# 128248
(09/01/16)

Source and Pharmacology:

CDX-011 is an antibody-drug conjugate (ADC) comprised of a fully-human IgG2 monoclonal antibody (CR011) directed against glycoprotein NMB (GPNMB) and conjugated to the tubulin-binding cytotoxic agent monomethylauristatin E (MMAE) via a protease-sensitive valine-citrulline linker and p-aminobenzoic acid (PABA) spacer. The average MMAE: antibody molar ratio is approximately 4.5:1. The antibody is manufactured by Chinese Hamster Ovary (CHO) cell culture, and the drug-linker combination vcMMAE is manufactured by chemical synthesis.

The proposed mechanism of action of CDX-011 is as follows: After the ADC binds to GPNMB on tumor cells, the complex is internalized and MMAE is released via proteolytic cleavage of the valine-citrulline linker in a lysosomal compartment. Tumor cell death occurs as a result of microtubule inhibition by MMAE with resultant cell cycle arrest.

Pharmacokinetics

[figure not shown]
A series of nine horizontal black bars of varying lengths, decreasing from top to bottom. Each bar is positioned above a white rectangular area.

[figure not shown]
Toxicity:

**Comprehensive Adverse Events and Potential Risks list (CAEPR)
for
CDX-011 (glembatumumab vedotin, NSC 763737)**

The Comprehensive Adverse Events and Potential Risks list (CAEPR) provides a single list of reported and/or potential adverse events (AE) associated with an agent using a uniform presentation of events by body system. In addition to the comprehensive list, a subset, the Specific Protocol Exceptions to Expedited Reporting (SPEER), appears in a separate column and is identified with bold and italicized text. This subset of AEs (SPEER) is a list of events that are protocol specific exceptions to expedited reporting to NCI (except as noted below). Refer to the 'CTEP, NCI Guidelines: Adverse Event Reporting Requirements' http://ctep.cancer.gov/protocolDevelopment/electronic_applications/docs/aeguidelines.pdf for further clarification. *Frequency is provided based on 255 patients.* Below is the CAEPR for CDX-011 (glembatumumab vedotin).

NOTE: Report AEs on the SPEER **ONLY IF** they exceed the grade noted in parentheses next to the AE in the SPEER. If this CAEPR is part of a combination protocol using multiple investigational agents and has an AE listed on different SPEERs, use the lower of the grades to determine if expedited reporting is required.

A series of six horizontal black bars of varying lengths, decreasing from left to right, set against a white background. The bars are positioned in a staggered, non-linear fashion, creating a sense of depth or a stylized representation of a landscape or data visualization.

Guidelines for Administration:

See Treatment and Dose Modification sections of the protocol for complete details. CDX-011 is diluted with D5W and administered as a 90-minute IV infusion using a 0.22 μ m low protein binding in-line filter. Patient should receive post-infusion flush with appropriate volume of D5W administered at the same rate as CDX-011 infusion.

Supplier:

Supplier: CDX-011 is supplied by Celldex Therapeutics and distributed by the Division of Cancer Treatment and Diagnosis (DCTD), NCI.

Obtaining the Agent

Agent Ordering

To comply with the timing requirement for study enrollment ([Section 3.1.5](#)), participating institutions are advised to plan ahead to ensure adequate and timely delivery of the investigational agent. Participating institutions may have to use their express courier account for overnight shipping when ordering the agent.

NCI supplied agent may be requested by the Principal Investigator (or their authorized designee) at each participating institution. Pharmaceutical Management Branch (PMB) policy requires that agent be shipped directly to the institution where the patient is to be treated. PMB does not permit the transfer of agents between institutions (unless prior approval from PMB is obtained). The CTEP assigned protocol number must be used for ordering all CTEP supplied investigational agents. The responsible investigator at each participating institution must be registered with CTEP, DCTD through an annual submission of FDA form 1572 (Statement of Investigator), Curriculum Vitae, Supplemental Investigator Data Form (IDF), and Financial Disclosure Form (FDF). If there are several participating investigators at one institution, CTEP supplied investigational agents for the study should be ordered under the name of one lead investigator at that institution.

Active CTEP-registered investigators and investigator-designated shipping designees and ordering designees must submit agent requests through the PMB Online Agent Order Processing (OAOP) application <https://eapps-ctep.nci.nih.gov/OAOP/pages/login.jspx>. Access to OAOP requires the establishment of a CTEP Identity and Access Management (IAM) account <https://eapps-ctep.nci.nih.gov/iam/> and the maintenance of an “active” account status and a “current” password. For questions about drug orders, transfers, returns, or accountability, call [contact] Monday through Friday between 8:30 am and 4:30 pm (ET) or email [contact] anytime.

Agent Accountability

Agent Inventory Records:

The investigator, or a responsible party designated by the investigator, must maintain a careful record of the inventory and disposition of all agents received from DCTD using the NCI Drug Accountability Record Form (DARF). See the CTEP home page at <http://ctep.cancer.gov> for the Procedures for Drug Accountability and Storage and to obtain a copy of the DARF and Clinical Drug Request form.

Agent Returns:

Investigators/Designees must return unused DCTD supplied investigational agent to the NCI clinical repository as soon as possible when: the agent is no longer required because the study is completed or discontinued and the agent cannot be transferred to another DCTD sponsored protocol; the agent is outdated or the agent is damaged or unfit for use. Regulations require that all agents received from the DCTD, NCI be returned to the DCTD, NCI for accountability and disposition. Return only unused vials/bottles. Do NOT return opened or partially used vials/bottles unless specifically requested otherwise in the protocol. See the CTEP web site for Policy and Guidelines for Investigational agent Returns at: http://ctep.cancer.gov/protocolDevelopment/default.htm#agents_drugs. The appropriate forms may be obtained at: http://ctep.cancer.gov/forms/docs/return_form.pdf.

